5. AMENDMENTS AND UPDATES

Number	Date	Section of the study protocol	Amendment or update	Reason
1	12AUG16	Throughout the text of this protocol.	Amendment	To reflect the change of Sponsor from Novartis Vaccines and Diagnostics Inc. to GlaxoSmithKline Biologicals S.A.
1	12AUG16	page 1	Amendment	EU PAS register number has been added in the coversheet.
1	12AUG16	Throughout the text of this protocol.	Amendment	The name of the vaccine (BEXSERO) has been capitalized.
1	12AUG16	Annex 2 ENCEPP CHECKLIST	Amendment	ENCePP Checklist updated and attached to this protocol.

6. MILESTONES

Table 6-1 Overview of study milestones.

Milestone	Planned date
Start of data collection	31 January 2016
End of data collection	The pregnancy registry will continue enrolling exposed pregnancies for a period of 3 years (final enrollment: 31 January 2019) and subsequent follow-up of enrolled infants will continue until 30 November 2019 (maximum 10 months follow-up post enrolment) or pending CBER review and discussion of results with GSK.
Annual updates	Annual interim reports will be provided to CBER per the PMC.
Final report of study results	A final report will be produced approximately 6 months after all data have been collected and cleaned and will be submitted to CBER by 31 May 2020.

Abbreviations: CBER = Center for Biologics Evaluation and Review; IRB = institutional review board; GSK = GlaxoSmithKline Biologicals S.A.

7. RATIONALE AND BACKGROUND

The gram-negative bacterium *Neisseria meningitidis* is the most common cause of bacterial meningitis in children and young adults in developed countries (Khatami, 2010). For the majority, exposure results in asymptomatic nasopharyngeal carriage. For those who develop invasive meningococcal disease (IMD), the disease spectrum ranges in severity from mild influenza-like illness to meningoenzephalitis, prostration, and death in 10% to 15% of patients. Long-term side effects including neurological deficit, limb amputation, hearing loss, blindness, and skin scarring can occur in up to 20% of cases (Edmond, 2010).

Six major meningococcal serogroups are associated with invasive disease: A, B, C, W, X, and Y (Stephens 2007a). Serogroup prevalence varies with geography, time of year, and age group. Serogroups B, C, and Y strains are currently the most prevalent in North America (Stephens, 2007b), while serogroup B and C strains are the most prevalent in Europe (ECDC, 2015); serogroup A strains (which have largely disappeared from Europe and North America) are responsible for large annual epidemics of bacteremia and meningitis in sub-Saharan Africa (WHO, 2014). Serogroups W and X meningococci have been responsible for epidemics in sub-Saharan Africa since 2002 (Stephens, 2007).

The incidence of IMD in the United States (US) has fluctuated cyclically since the early 1970s, ranging from 0.5 to 1.5 cases per 100,000 population. Since 1996, the incidence has declined sharply and in 2012 the incidence was 0.18/100,000, serogroup B accounting for 0.04/100,000 cases (Adams, 2014). The incidence is highest in infants aged <1 year, with a second peak occurring in adolescents and young adults (Cohn, 2013). Most IMD cases are sporadic, but between 2009 and 2015, there were 32 cases of serogroup B meningococcal disease associated with outbreaks at 5 US universities, including 1 fatality (MacNeil, 2015).

Since 2010, routine use of quadrivalent meningococcal conjugate vaccine covering serogroups A, C, W, and Y is recommended in the US for adolescents and others at increased risk for meningococcal disease (Cohn, 2013). More recently, vaccines against serogroup B disease have been approved by the Food and Drug Administration (FDA) for use in individuals 10 through 25 years of age (FDA, 2014; FDA, 2015). In February 2015, the Advisory Committee on Immunization Practices (ACIP) recommended that a meningococcal group B vaccine should be administered to persons in the US aged ≥ 10 years who are at increased risk for meningococcal disease. This includes persons with persistent complement component deficiencies (estimated at approximately 80,000 persons in the US), persons with anatomic or functional asplenia (approximately 100,000 persons), microbiologists routinely exposed to isolates of *Neisseria meningitidis* (approximately 100,000 persons), and persons identified to be at increased risk because of a serogroup B meningococcal disease outbreak (approximately 60,000 between 2009 and 2013) (MacNeil, 2015).

BEXSERO was developed by to help confer protection against a broad range of meningococcal B strains causing disease. It is formulated with 3 major recombinant proteins (factor H binding protein, neisserial heparin binding antigen, and *Neisseria* adhesin A) combined with bacterial outer membrane vesicles derived from the New Zealand outbreak strain NZ98/254, containing PorA type P1.4 as the main antigen (Giuliani, 2006) and aluminium hydroxide as an adsorbent. In those aged 10 to 25 years, it should be administered in a 2-dose schedule (0.5 mL each), each dose at least 1 month apart (Bexsero[®] prescribing information, 2015).

and 2 during gestation) at a dose equivalent to the absolute human dose or 15 times the human dose on a body weight basis (4 kg in rabbits and 60 kg in humans). This study was designed to comply with FDA guidance on the testing of the developmental toxicity of vaccines, and according to International Conference on Harmonisation (ICH) Harmonised Tripartite Guideline (ICH, 1996) (stages A through E of the reproductive process, with the exception of determination of effects on estrous cycle). Evaluation of the maternal animals, their developing fetuses, and offspring for up to 4 weeks after birth demonstrated that BEXSERO was not a reproductive or developmental toxicant (Ching-Long, 2014). The vaccine was immunogenic in the maternal animals; circulating antibodies were detected in their fetuses and persisted in offspring through day 29 of lactation (ELISA and SBA with rabbit complement).

BEXSERO is not contraindicated during pregnancy, but according to the vaccine label, BEXSERO should be used during pregnancy only if clearly needed. Inadvertent exposure within 30 days prior to last menstrual period (LMP) or early in the first trimester (before pregnancy status is known) might be expected to occur because the age group targeted for the vaccine includes young women of reproductive potential. The BEXSERO Pregnancy Registry is established to meet a Center for Biologics Evaluation and Research (CBER) post-marketing commitment (PMC) and is designed to collect prospective data on pregnancy outcomes among women immunized with the BEXSERO vaccine within 30 days prior to LMP or at any time during pregnancy. The registry will add to the current clinical experience with BEXSERO, supplementing existing data from animal toxicology studies and human exposure data. Pregnancy data will be collected at registry enrollment and, where accessible, at the end of the second trimester of pregnancy, and at pregnancy outcome for both mother and infant. GSK will sponsor the registry in consultation with specialists from appropriate fields such as obstetrics, pediatrics, clinical research, genetics, epidemiology, and teratology from academic institutions, private practice, and/or government agencies. These individuals constitute the Scientific Advisory Committee (SAC) and will provide an independent review of registry data.

8. RESEARCH QUESTION AND OBJECTIVES

The objective of the BEXSERO Pregnancy Registry is to evaluate pregnancy outcomes among women immunized with the BEXSERO vaccine within 30 days prior to the LMP or at any time during pregnancy. The primary outcomes of interest include major congenital malformations (MCMs), preterm birth, and low birth weight (LBW).

Other pregnancy outcomes will be collected, including stillbirths and spontaneous abortions (SABs). The probability of SAB varies greatly as a function of when the pregnancy is enrolled in the registry ([Savitz, 2002](#)). Because pregnancies will be reported to the registry at different and imprecise times during gestation, calculation of the prevalence of SAB from the registry is deemed inappropriate and could lead to erroneous conclusions. For example, if a woman enrolls in the registry at 16 weeks of pregnancy, only an SAB after this time could be detected and included in prospective reports. Similarly, SABs occurring earlier in gestation may not have been recognized and/or reported.

This registry is primarily descriptive and designed to detect potential safety signals rather than test hypotheses.

9. RESEARCH METHODS

9.1 Study Design

The BEXSERO Pregnancy Registry is a prospective, observational study of pregnant women immunized with the BEXSERO vaccine within 30 days prior to LMP or at any time during pregnancy. It is strictly observational; the schedule of office visits and all treatment regimens will be determined by the treating health care provider (HCP). The registry will collect data that are routinely documented in the patient's medical record in the course of usual care.

The design of this pregnancy registry follows current FDA guidance for designing and implementing pregnancy exposure registries (FDA, 2002).

9.2 Setting

Not applicable.

9.2.1 Study Period

The pregnancy registry will be implemented after approval by the applicable regulatory authority and central institutional review board (IRB). The data collection process for each participant will begin at enrollment (during pregnancy), follow-up will occur (pending ongoing cooperation by the woman and her HCP) at the end of the second trimester (approximately 24 weeks' gestation) and at pregnancy outcome (delivery or early termination).

9.2.2 Study Subjects

The study population will include pregnant women within the US who received at least 1 dose of BEXSERO vaccine (confirmed or possible exposure) within 30 days prior to LMP or at any time during pregnancy. BEXSERO should be used during pregnancy only if clearly needed, but inadvertent exposure during pregnancy might be expected because the age group targeted for the vaccine includes young women of reproductive potential.

9.2.3 Study Population Selection

The minimum criteria required for enrollment into the registry are as follows:

- Sufficient evidence to confirm that exposure to a serogroup B meningococcal vaccine (confirmed or possible BEXSERO vaccination) occurred within 30 days prior to LMP or at any time during pregnancy

- Sufficient information to determine whether the pregnancy is prospectively or retrospectively registered (i.e., whether the outcome of pregnancy was known at the time of first contact with the registry)
- Date the pregnancy exposure is registered
- Full reporter (i.e., HCP) contact information to allow for follow-up (name, address, etc.)

In the event that it cannot be ascertained to which meningococcal B vaccine the woman was exposed, an unknown exposure cohort will be established and analyzed separately.

Enrollment in the Registry

[figure not shown]
Enrollment and data collection will be coordinated through a registry coordination center (RCC) staffed by trained registry coordinators located in the US. These registry coordinators will be the first line of communication with participants and their HCPs. The coordinators are experienced in working directly with both patients and HCPs to establish a rapport with them and assist them in fulfilling registry requirements. The team will be formally trained in the appropriate methods for handling registry calls with scripts and decision trees in place. Please also refer to [Section 10.3](#) for additional details of the RCC.

Eligible pregnant women may be enrolled in various ways. They may self-enroll in the registry by calling the pregnancy registry telephone number directly or their HCP can, with their consent, enroll them on their behalf. Alternatively HCPs may report de-identified data on pregnancy exposures and outcomes occurring within their network/health maintenance organization (HMO).

[Figure 9.2.3-1](#) outlines the process flow for enrolling registry participants under the 3 models:

1. Self-enrollment with signed informed consent or verbal consent (waiver of documentation of informed consent)
2. HCP enrollment with signed informed consent or verbal consent (waiver of documentation of informed consent)
3. De-identified data provided by HCPs under the waiver of informed consent provision.

Figure 9.2.3-1 Registry enrollment, informed consent and data collection process

Abbreviations: HCP = health care provider; ICF = informed consent form; PI = principal investigator; RCC = registry coordination center.

Registry Awareness and Recruitment

Because registry enrollment is open to all eligible pregnant women, an active recruitment campaign will reach out to immunization providers and their patients in a broad variety of settings. The recruitment strategy will target HCPs who are known to immunize patients specifically with the BEXSERO vaccine. This might include OBGYN consultants and other specialists attending high-risk groups as defined by the ACIP recommendation (MacNeil, 2015). These providers could be identified through GSK BEXSERO distribution data and/or medical science liaisons (MSLs), as well as HCP networks and HMOs.

This targeted awareness will include the distribution of a comprehensive informational kit designed to solicit interest among pregnant women in registry participation. All messaging will be in line with product labeling.

The kit may include:

- Branded registry information sheet and/or brochure that will briefly describe the registry purpose and procedures
- Enrollment form and sample patient consent form
- Prescribing information
- Participant consent to contact card (this card enables the RCC to contact the potential patient and provide additional information about the registry)

Persistent awareness activities incorporating the above awareness materials as well as a variety of other approaches such as internet, product labeling, or messaging by MSLs may also be used, for example:

- Internet:
 - FDA listing of pregnancy registries on www.fda.gov
 - www.clinicaltrials.gov
 - Society for Maternal-Fetal Medicine listing of registries
 - PPD website
 - GSK website)
- Print:
 - BEXSERO prescribing information
 - BEXSERO medication guide
 - Medical journal advertising and/or direct to physician advertising

- Registry contact information in report(s)
- Education:
 - MSL outreach to treating HCPs
 - Scientific presentations and publications
 - Distribution of report(s) to HCPs

Reference Groups

Given the inherent difficulties in identifying a comparison group (Covington, 2009), several different methods may be used to review the data for safety signals. As described below, background prevalence estimates from external surveillance sources and estimates from published literature will be the primary comparators. To the extent possible, comparator prevalence estimates will be age-adjusted to reflect the age distribution of the BEXSERO Pregnancy Registry population.

Background Prevalence Estimates of Pregnancy Outcomes

Background prevalence estimates in the general population of pregnancy outcomes, such as premature birth and LBW, are readily available from national vital statistics or publications in the scientific literature (Martin, 2015).

Background Prevalence Estimates of Major Congenital Malformations (MCMs)

Published prevalence estimates of MCMs are available from the CDC's Metropolitan Atlanta Congenital Defects Program (MACDP), which is an ongoing population-based birth defects surveillance program (Correa, 2007). The primary objectives of MACDP are to regularly and systematically monitor births of malformed infants for changes in incidence or other unusual patterns suggesting environmental influences, and to develop a case registry for use in epidemiological studies. MACDP actively searches for MCMs among the 50,000 annual births to residents of metropolitan Atlanta's 5 counties and abstracts medical records at all Atlanta obstetric hospitals, Atlanta pediatric referral hospitals, genetics labs, and vital records (Correa-Villasenor, 2003). While there are inherent problems with comparing data from women exposed to specific vaccines in pregnancy with background prevalence estimates from the general population, this is not an unrealistic comparison (Honein, 1999), and background estimates may be the only practical comparator. MACDP has been used as a comparator by over 60% of pregnancy registries identified in a recent survey (Covington, 2009).

Background Prevalence Estimates from Literature or Other Studies

The registry is committed to identifying other appropriate comparison groups, and research of the literature and other sources, such as other pregnancy registries or observational studies, will continue in order to obtain appropriate background prevalence estimates.

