According to the CDC MACDP, the prevalence of MCMs for mothers <25 years of age in the US is 2.54% (Correa, 2007). According to the CDC National Vital Statistics System (NVSS), the prevalence of preterm birth and LBW for mothers <25 years of age are 11.71% and 8.50%, respectively (Martin, 2015).

The table below depicts sample sizes of 5, 20, 50, 100, and 150 live births and the associated effect sizes (i.e., the ratio of the registry-derived prevalence versus the reference prevalence) that would be detectable using a binomial distribution, a power of 80%, and a 1-sided Type I (false positive) error rate of 5% (Altman, 1991). For example, with a sample size of 100 live births, the study will have 80% power to detect a 1.79-fold

increase in the prevalence of preterm birth compared with the reference of 11.71% (population prevalence). In other words, if the registry-derived prevalence estimate is at least 1.79 times higher than the reference prevalence of preterm birth, the 1-sided 95% confidence interval for the estimate will exclude 11.71% (i.e., will lie above 11.71%), with a probability of 80%.

Table 9.5-1 Detectable effect size assuming 80% power

Sample size (N of live births)	Effect size (ratio of the registry-derived prevalence versus the reference prevalence for mothers <25 years of age)		
	MCM [reference = 2.54%]	PTB [reference = 11.71%]	LBW [reference = 8.50%]
5	19.30	5.75	7.92
20	7.95	3.13	3.69
50	4.23	2.24	2.59
100	3.07	1.79	1.96
150	2.66	1.63	1.82

Abbreviations: LBW = low birth weight; MCM = major congenital malformations; PTB = preterm birth.

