Formulas for the calculation of prevalence of the primary outcomes are presented below:

$$\begin{aligned} \text{MCM prevalence} &= \frac{\text{Number of live births and fetal losses occurring at } \geq 20 \text{ weeks gestation with MCM}}{\text{Number of live births (all fetal losses excluded from denominator per MACDP convention)}} \\ \text{Preterm birth prevalence} &= \frac{\text{Number of preterm live births}}{\text{Number of live births}} \\ \text{LBW prevalence} &= \frac{\text{Number of LBW live births}}{\text{Number of live births}} \end{aligned}$$

The MCM outcome data will be stratified by the earliest trimester of exposure to BEXSERO[®]. For this registry, gestational weeks are estimated from the most reliable EDD as reported by the HCP. If a CEDD is provided by the HCP, it will be used instead. The date of conception will be calculated as the most reliable EDD minus 38 weeks. If the EDD is not available or never estimated, the first day of the LMP may be used to estimate gestational age. The second trimester will be considered to begin at week 14, and the third trimester, at week 28. If there is a discrepancy between gestational age calculated from the LMP and reported gestational age, the HCP will be asked to verify the data.

If it is feasible, descriptive comparisons between the registry and an appropriate internal and/or external comparison group will be examined (see Section 9.2.3 for a description of potential reference groups).

Methods to Control for Confounding and Effect Modification

For analyses of associations between pregnancy outcomes and BEXSERO exposure, confounding and effect modification will be evaluated descriptively. A detailed description of these analyses will be available in the SAP. Potential confounders/effect modifiers may include the following:

- Maternal characteristics (e.g., age, ethnicity, race)

- Previous pregnancy outcomes (e.g., MCMs, stillbirth)
- Pregnancy complications (e.g., preterm labor, eclampsia, placental abruption)
- Comorbidities (e.g., diabetes, hypertension)
- Concomitant exposures (e.g., medications, alcohol, tobacco)
- Infant/fetus sex

Subgroup Analyses

Analyses will be stratified by trimester of exposure and other subgroups of interest, potentially including number of doses of BEXSERO received, gestational age at enrollment and maternal age. Additional details on subgroup analyses will be described in the SAP. Comparisons may be made to external cohorts, if appropriate.

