9.9 Limitations of the Research Methods

Since participation in the registry will be accomplished in 3 ways (through voluntary self-enrollment by the pregnant women, through HCP enrollment on behalf of the woman with her consent, or finally, through the collection of de-identified data from HCPs within a network/HMO), the included subjects may not be representative of the overall population of US pregnant women. If possible, a sensitivity analysis will be conducted according to pregnant women's method of enrollment: the data collected from pregnant women who provide consent and either self-enroll or authorize their HCPs to enroll them in the registry will be examined separately from the de-identified data collected from HCPs on pregnancy exposures and outcomes within a network/HMO.

Additionally, it is possible that even in prospectively reported cases, potential bias could exist. For example, high-risk pregnancies or low-risk pregnancies may be more likely to be reported. It is also possible, and entirely likely, that differences in the prevalence estimates of pregnancy outcomes will be observed due to random variability (NBDPN, 2004). With the prevalence of the outcomes of interest being relatively low, cases of a particular outcome can be expected to be quite rare, and the coincidence of 2 or more cases in time may be just that: a coincidence. Confidence intervals will be carefully examined in order to assess the potential role of random variability.

Furthermore, it will be important to rule out other explanations for changing prevalence over time, including changes in medical diagnoses and technologies, changes in reporting and case ascertainment, and changes in the population at risk. In order to minimize the effect of these changes, the most current prevalence estimates available at the time of reporting for the population of interest will be used for analyses.

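### A cheap improvement: beside the age-adjusted preterm birth and low birth weight references, pre-specify one weighted to the registry's joint age and race/ethnicity mix

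*Combined protocol and SAP*

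**What the plan says.** Section 9.2.3 (Reference Groups) names external surveillance and literature prevalences as the primary comparators and adds: "To the extent possible, comparator prevalence estimates will be age-adjusted to reflect the age distribution of the BEXSERO Pregnancy Registry population". The abstract says the same. No other standardization of the reference is described.

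Section 9.3.3 collects maternal age, ethnicity and race, and section 9.4 places them on the registration form. Section 9.7.3 lists the three together among factors that may be confounders or effect modifiers. It says that "confounding and effect modification will be evaluated descriptively" and leaves the detail to the SAP. Section 9.7.2 adds a review of baseline data for factors that could affect how the comparisons are interpreted. Section 9.9 concedes that "the included subjects may not be representative of the overall population of US pregnant women".

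The planning references are in section 9.5: "the prevalence of preterm birth and LBW for mothers <25 years of age are 11.71% and 8.50%, respectively". The same section gives the intended reading: "with a sample size of 100 live births, the study will have 80% power to detect a 1.79-fold" increase in preterm birth, in the sense that the 1-sided 95% interval lies wholly above 11.71%.

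**The concern.** With no guaranteed internal control, the comparison rests on the external reference. Adjusting it for age accepts that it should reflect who is in the registry, and the text gives no reason for stopping at age when race and ethnicity are to hand.

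A descriptive table of race and ethnicity tells the reader that the mix differs. It does not say what prevalence that mix would produce without any vaccine effect. If the true no-effect prevalence is above the age-adjusted reference, the bound lies above it too often. If it is below, a real increase is more easily missed, which in a safety registry is the more troublesome error. Regression is not a realistic remedy at 5 to 150 live births. Weighting published external rates needs only the registry's mix.

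**Working it through.** **Inputs from section 9.5.** References p0 = 11.71% (preterm birth) and 8.50% (LBW); 5, 20, 50, 100 or 150 live births; 1-sided 5%; 80% power; exact one-sample binomial (section 9.6.2).

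**Step 1: reproduce the plan's figure.** The cut-off r is the smallest count with P(X ≥ r | n, p0) ≤ 0.05. The detectable ratio is p1/p0, where P(X ≥ r | n, p1) = 0.80.
- Preterm, n = 100: r = 18, exact probability 4.18%, ratio 1.789 (table: 1.79).
- LBW, n = 100: r = 14, exact probability 4.37%, ratio 1.961 (table: 1.96).

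The exact 1-sided lower bound gives the same preterm cut-off: 18/100 has a bound of 11.97%, above 11.71%, and 17/100 has 11.13%, below it. All 15 cells of Table 9.5-1 reproduce to within 0.01, so the sizing arithmetic is sound.

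**Step 2: assumed case mix (not in the documents).** Two groups within age, with prevalence ratio R = 1.3 or 1.5. The higher-prevalence group is s0 = 20% or 25% of the reference population and s1 = 5%, 40% or 50% of the registry. The no-effect prevalence in the registry is

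p_reg = p0 × [1 + s1(R − 1)] / [1 + s0(R − 1)].

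Example: R = 1.5, s0 = 20%, s1 = 50% gives 11.71% × 1.25 / 1.10 = 13.31%.

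**Step 3: chance that the bound lies above 11.71% with no vaccine effect.** This is P(X ≥ 18 | 100, p_reg), for preterm birth. Each cell gives p_reg, then the probability.

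| R | s0 | s1 = 5% | s1 = 40% | s1 = 50% |
|---|---|---|---|---|
| 1.3 | 20% | 11.21%; 2.89% | 12.37%; 6.50% | 12.70%; 7.95% |
| 1.3 | 25% | 11.06%; 2.55% | 12.20%; 5.83% | 12.53%; 7.15% |
| 1.5 | 20% | 10.91%; 2.27% | 12.77%; 8.29% | 13.31%; 11.12% |
| 1.5 | 25% | 10.67%; 1.85% | 12.49%; 7.00% | 13.01%; 9.48% |

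The planned value is 4.18%. At s1 = 5%, power for a true 1.79-fold increase over p_reg falls from 80% to between 64.9% and 73.5%. If R = 1 or s1 = s0, nothing changes.

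For LBW at n = 100, the same assumptions give 5.8% to 10.1% (s1 = 40% to 50%) and 2.2% to 3.2% (s1 = 5%), against 4.4%.

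**Step 4: other sizes, preterm birth, all 12 scenarios.**

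| n | r at 11.71% | Planned | Range | r if the reference is matched |
|---|---|---|---|---|
| 5 | 3 | 1.3% | 1.0–1.9% | 3 |
| 20 | 6 | 2.3% | 1.5–4.1% | 6 |
| 50 | 11 | 2.8% | 1.5–6.2% | 10–12 |
| 100 | 18 | 4.2% | 1.9–11.1% | 17–20 |
| 150 | 25 | 4.4% | 1.6–13.8% | 23–28 |

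**Step 5: effect of a matched reference at n = 100.** With the cut-off taken from p_reg, the no-effect probability is 2.9% to 4.9% in every scenario. Power for the 1.79-fold increase is 73.5% to 85.1%. In practical terms, a count of 18/100 (bound 11.97%) lies above 11.71% but below every p_reg in the 40% and 50% columns, so the reading changes.

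**The case against.** Four arguments carry weight.

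1. **A reader might infer that the plan has a preterm/LBW decision rule whose error rate is broken.** The documents do not support that. Section 9.7.1 calls the registry primarily descriptive. The criterion that the interval lie above the reference appears in the sizing text, and the only explicit signal convention (section 9.4.5) concerns malformations. The probabilities above describe how often a reported bound would look like an excess; they are not a trial-level Type I error. It remains true that the 1-sided bound is reported in order to detect a prevalence above the reference, so a mismatched reference can mislead a descriptive reader too.

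2. **A reader might infer that the registry's mix is known to differ.** It is not. The caveat in section 9.9 concerns enrollment routes and does not mention race or ethnicity. No group-specific prevalence or expected mix is given, so existence, direction and size are all assumptions.

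3. **The plan already does part of this.** It reviews baseline data, evaluates confounding descriptively with SAP detail, looks for further comparison groups, and will use the most current prevalences. So 11.71% and 8.50% are planning values. This stands, but none of these steps commits to adjusting the reference beyond age, and the same gap would apply to updated figures.

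4. **Feasibility and scope.** The documents do not say whether the sources publish joint age-by-race/ethnicity rates. Comorbidities, tobacco and previous pregnancy outcomes would remain unadjusted. Accrual may be too low for the change to matter. All of this stands, and it argues for a companion comparison and against replacing the planned one.

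**Conclusion.** The point holds as a low-cost improvement, not as a demonstrated bias. The reference is adjusted for age only, while two other collected factors named beside age are left to description. Under the stated assumptions, at 100 live births the chance of the bound lying above the preterm reference with no vaccine effect is about 5.8% to 11% for registry shares of 40% to 50%, and 1.9% to 2.9% for a share of 5%, against 4.2%. The LBW figures are similar. The shift is zero if the mixes match or if prevalence does not vary by race/ethnicity within age. At 5 or 20 live births a matched reference leaves the cut-off where it is. The calculation covers preterm birth and LBW only and does not call Table 9.5-1 into question.

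**What to change.** In sections 9.2.3 and 9.7.3, keep the age-adjusted comparison and pre-specify a second reference beside it for preterm birth and LBW. Weight the source's current stratum prevalences by the registry's joint age and race/ethnicity distribution of live births, wherever the source publishes those strata. Use the age-specific rate alone for infants whose mother's race or ethnicity is missing, or where the strata are unavailable. Report the 1-sided 95% bound against the crude, the age-adjusted and the age-and-race/ethnicity-adjusted references, and state the registry's mix next to them.

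The cost is a few sentences and one weighting table, with no new data collection. The drawbacks are dependence on what the source publishes and the confounders that this leaves unaddressed; the report should name them.
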